11.3 Study Design

The primary cohort defined below will employ single stage A'Hern designs of N=20 and N=10 respectively. The agent will be deemed worthy of further study in the relevant subset of patients (i.e. biomarker positive in any histology, biomarker positive in a particular histology, etc) if the decision rule is met. Operating characteristics are shown below.

Cohort	N	Decision Rule	Alpha	Power
Primary biomarker positive	20	≥ 3 responses	10%	90%

Histology-specific biomarker positive expansion cohorts will, by definition, be deemed worthy of further study, since they will have at least 3 responses. The table below shows 90% confidence intervals (Wilson method) for a range of observable response rates.

Cohort Size	Observed Response Rate	90% Confidence Interval
10	30%	13% - 56%
10	40%	19% - 65%
10	50%	27% - 73%

11.3.1 Primary Cohort:

APEC1621J will evaluate a primary cohort of 20 mutation-matched (“biomarker positive”) evaluable patients of any histology for the primary study aim of determining the objective response rate (CR/PR according to the response criteria in Section 12.3) to the agent. Using an A'Hern design²⁹ with alpha=10%, a sample of N=20 will provide 90% power to detect an improvement in response rate from 5%, if the treatment is ineffective, to 25% if the targeted therapy is sufficiently effective to warrant further study. If there are at least 3 responses out of 20 in the primary cohort, the biomarker/therapy match will be deemed a success.

11.3.2 Histology-Specific Biomarker Positive Expansion Cohorts:

If ≥ 3 patients in the primary cohort with the same histology show signs of objective response (CR/PR according to the response criteria in Section 12.3), a histology-specific biomarker positive expansion cohort will open after the primary cohort is completed to up to 7 evaluable patients for a total sample size of 10 evaluable biomarker positive patients with that histology. This will allow us to estimate more precisely the activity in biomarker positive patients of that histology. See Appendix VII for a list of target tumor histologies.

We will open up to 3 such expansion cohorts for biomarker positive patients (i.e., if 3 histologies have ≥ 3 responses, we will open a total of 3 expansion cohorts as described above). Note that this can only happen if the response rate in the primary cohort is at least 45% (9/20) and there cannot be more than 21 additional evaluable patients in total for these expansion cohorts.

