2.5 Overview of Proposed Pediatric Study

This is a phase 2 trial of BVD-523FB (ulixertinib) in children with recurrent or refractory solid tumors, CNS tumors, non-Hodgkin lymphomas and histiocytic disorders harboring specific activating mutations that result in pathologic activation of the MAPK pathway.

Because the pediatric dose of BVD-523FB (ulixertinib) has not been established, there will be a limited dose finding phase consisting of the first 12 evaluable patients enrolled on study. BVD-523FB (ulixertinib) will be administered for 28-day cycles twice daily per nomogram by mouth on an empty stomach. The first 6 evaluable patients will be enrolled at a dose of 260 mg/m²/dose BID (450 mg BID Max Dose), equivalent to 75% of the maximum tolerated dose (MTD) in adults. There will be a single dose escalation to 350 mg/m²/dose BID (100% of the adult MTD [600 mg BID Max Dose]) or de-escalation to 175 mg/m²/dose BID (50% of the adult MTD [300 mg BID Max Dose]) for the next six subjects. Following the first 12 evaluable patients, all subsequent patients will be enrolled at the highest dose level not exceeding the pediatric MTD. Patients enrolled in the dose escalation component will be included in the analysis of efficacy.

The primary aim of this trial will be to establish the objective response rate to BVD-523FB (ulixertinib). While there will not be multiple pre-determined mutation-based cohorts, responses will be analyzed retrospectively with respect to specific MAPK pathway activating mutations.

Key secondary objectives include further evaluation of the tolerability of BVD-523FB (ulixertinib) in pediatric patients. Toxicity will be assessed using CTCAE V5.0. Imaging for disease evaluation will occur every other cycle x 3, then every three cycles. Disease response will be assessed according to RECIST v1.1 for solid tumors and 2-dimensional measurement for CNS tumors.

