11.4 Methods of Analysis

Response criteria are described in Section 12. A responder is defined as a patient who achieves a best response of PR or CR on the study. Response rates will be calculated as the percent of evaluable patients who are responders, and confidence intervals will be constructed using the Wilson score interval method.³⁰ Decision making for A'Hern design cohorts will follow rules described above.

Any responses or lack thereof in patients enrolled during the determination of the Recommended Phase 2 Dose (dose finding phase) will count toward the objective response rate in their respective cohort.

Toxicity tables will be constructed to summarize the observed incidence by type of toxicity and grade. A patient will be counted only once for a given toxicity for the worst grade of that toxicity reported for that patient. Toxicity information recorded will include the type, severity, time of onset, time of resolution, and the probable association with the study regimen.

11.5 **Evaluability for Response**

Any eligible patient who is enrolled and receives at least one dose of protocol therapy will be considered evaluable for response. Any patient who receives non-protocol anti-cancer therapy during the response evaluation period will be considered a non-responder for the purposes of the statistical rule, unless they show an objective response prior to receiving the non-protocol anti-cancer therapy (in which case they will be considered a responder). Patients who demonstrate a complete or partial response confirmed by central review will be considered to have experienced a response. When opening expansion cohorts, the evaluation period for determination of best response will be 6 treatment cycles. All other patients will be considered non-responders. Patients who are not evaluable for response evaluation may be replaced for the purposes of the statistical rule. All patients considered to have a response (CR or PR) must have imaging studies reviewed centrally at the COG. Centers will be notified by the COG about requests for scans of patients with stable disease. Preliminary assessment of activity using institutionally provided tumor measurements will be entered into CDUS quarterly. The central review by COG will be provided as the final reviewed assessment of response when such becomes available.

11.6 **Evaluability for Toxicity**

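### Histology expansion cohorts: the 10 patients include the 3 or more responders that opened the cohort, so the reported response rate is biased upward and its Wilson 90% interval under-covers at low to moderate true rates

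*Combined protocol and SAP*

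**What the plan says.** Section 11.3.2 opens an expansion cohort for a histology when 3 or more primary-cohort patients with that histology respond. Enrolment then continues for "up to 7 evaluable patients for a total sample size of 10 evaluable biomarker positive patients with that histology". At most three such cohorts may open. The stated purpose is estimation: "This will allow us to estimate more precisely the activity in biomarker positive patients of that histology".

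On the go decision, section 11.3 says: "Histology-specific biomarker positive expansion cohorts will, by definition, be deemed worthy of further study, since they will have at least 3 responses". On the estimate, it says: "The table below shows 90% confidence intervals (Wilson method) for a range of observable response rates". The table, for a cohort of 10, gives 13%-56% at an observed 30%, 19%-65% at 40% and 27%-73% at 50%. Section 11.4 defines the response rate as responders over evaluable patients and adds that "confidence intervals will be constructed using the Wilson score interval method".

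Sections 11.3 to 11.5 contain no allowance for the opening rule, no separate display of the new patients, and no caveat on the pooled rate or interval. Section 11.3 also announces: "The primary cohort defined below will employ single stage A'Hern designs of N=20 and N=10 respectively". Alpha and power are given for N=20 only.

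**The concern.** A cohort that exists only because it already has 3 responders cannot show fewer than 3 of 10. The responders/10 estimator and the Wilson interval both treat the 10 as an unselected sample. Given that the cohort opened, the reported rate is therefore too high on average. The interval is shifted upward with it.

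The go decision is settled at opening, so what expansion adds is the estimate and its precision. If a histology-specific rate is later used to plan a follow-on study, its readers would see a rate and a 90% interval with no sign that the data that opened the cohort are also the data being summarised.

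**Working it through.** **Inputs from the documents.** Opening rule: at least 3 responders of the histology in the primary cohort (11.3.2). Denominator: 10 including those patients (11.3.2). Interval: Wilson, 90% (11.3, 11.4). Target rate: 25% (11.3.1; set for the any-histology primary cohort and used here as a reference value).

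**Assumptions.** m, the number of primary-cohort patients of that histology, is not in the documents; a range is shown. Primary-cohort and new patients share one true rate p, except in the last step.

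**1. The plan's own table.** The Wilson interval is [p̂ + z²/2n ± z√(p̂(1−p̂)/n + z²/4n²)] / (1 + z²/n), with z = 1.645 and n = 10. At 3/10 this is (0.300 + 0.135 ± 1.645 × 0.1666)/1.271 = 12.7% to 55.8%. At 4/10 it is 19.4% to 64.8%, and at 5/10 it is 26.9% to 73.1%. All three rows of the table reproduce. The arithmetic is right; the issue is its application to a selected cohort.

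**2. Model given opening.** X1 ~ Bin(m, p) restricted to X1 ≥ 3, X2 ~ Bin(10 − m, p), T = X1 + X2. The mean reported rate is [E(X1 | X1 ≥ 3) + (10 − m)p]/10. Coverage is the probability, given opening, that the Wilson interval for T/10 contains p.

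**3. True rate 25%.** Among the possible results (T ≥ 3), only 3/10 and 4/10 have a lower limit below 25%, so coverage is P(T=3) + P(T=4). No interval can lie wholly below 25%, because the upper limit at 3/10 is already 55.8%. Every miss is therefore above the true rate.

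| m | P(open) | E(X1 given X1 ≥ 3) | Mean reported rate | Coverage |
|---|---|---|---|---|
| 5 | 10.4% | 3.160 | (3.160 + 1.25)/10 = 44.1% | 0.2015 + 0.3694 = 57.1% |
| 8 | 32.1% | 3.453 | (3.453 + 0.50)/10 = 39.5% | 0.3633 + 0.3936 = 75.7% |
| 9 | 39.9% | 3.566 | (3.566 + 0.25)/10 = 38.2% | 0.4387 + 0.3656 = 80.4% |
| Unselected n = 10 | – | – | 25% | 86.6% |

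The extreme m = 3 gives a mean of 47.5% and coverage of 44.5%, but opens with probability only 1.6%.

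**4. Removing discreteness.** The unselected interval itself covers only 86.6% at exactly 25%. Averaged evenly over true rates of 20% to 30%, coverage is 67%, 82% and 86% for m = 5, 8 and 9, against 90% unselected.

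**5. Where the problem fades.** At a true 30%, coverage is 77% (m=5), 89% (m=8) and 91% (m=9). At 40% it is 84% (m=5), 91% (m=7), 92% (m=8) and 93% (m=9). Some upward bias remains: at 40% with m=8 the mean is 47.3%.

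**6. Unequal rates.** Section 11.4 says outcomes of dose-finding patients "will count toward the objective response rate in their respective cohort", so patients on different dose levels may be pooled and one common rate is not guaranteed. With m=8, primary 20% and new 25% give a mean of 38.3% against a true mix of 0.8×20 + 0.2×25 = 21%. Primary 25% and new 30% give 40.5% against 26%. Primary 25% and new 20% give 38.5% against 24%. Upward bias persists in all three. Coverage of the new-patient rate is 80%, 93% and 79%, so the size of the coverage loss does depend on this assumption.

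**The case against.** The strongest reply is that this is small and partly disclosed. The plan says that opened cohorts have at least 3 responses, its table starts at an observed 30%, at most three cohorts can open, and no decision rule uses the interval. All of that stands and keeps the severity modest. But the disclosure is used to justify the go decision; nothing qualifies the estimate or its interval.

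A second reply is that the size rests on inputs outside the documents. This is fair: m and the histology-specific true rate are both unknown, and 25% is a poor point for the Wilson interval even without selection. The averaged figures in step 4 answer the discreteness point. The dependence on m has to be stated, not removed.

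A third is that conditioning on opening is only one frame. If unopened histologies were also reported as responders/m, overall coverage at 25% would be 96%, 92% and 85% for m = 5, 8 and 9. That is correct, but a reader of an opened cohort's result is looking at a cohort that did open.

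Three stronger readings are tempting and are not supported:

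- A reader might infer that the efficacy decision is compromised. It is not. The primary rule is fixed on 20 patients (exact alpha 7.5%, power 90.9%), and the histology go decision is openly tied to the trigger.
- A reader might take N=10 as a test that cannot fail. The operating-characteristics table lists only N=20, and the text treats success as met at opening, so this is loose drafting.
- A reader might conclude that an interval conditional on opening must replace Wilson. A conditional mid-p version has its own faults: at 3/10 with m=3 it runs 0-28% and excludes the observed 30%, and its coverage ranges from about 82% at isolated true rates to 95-97% averaged over 20-30%. The count used at opening (response within 6 cycles, section 11.5) can also differ from final best response on study (section 11.4).

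**Conclusion.** The concern holds for the contingent histology-specific estimates. Given opening, responders/10 is biased upward. At a common true rate of 25% the bias is about 19, 15 and 13 points for m = 5, 8 and 9, and the nominal 90% interval covers 57%, 76% and 80% of the time, against 86.6% unselected. Over true rates of 20-30% the shortfall from the unselected 90% is about 23, 8 and 4 points. At 25% all the error is in the favourable direction.

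The direction of the bias follows from the opening rule. Its size rests on the assumed m and, for coverage, on primary-cohort and new patients sharing one rate. The unequal-rate results are for m=8 only and should not be read as a fixed bias for every cohort. Under-coverage essentially disappears at 30% with m of 8 or more and at 40% with m of 7 or more. The change is worth making because it costs little and serves the stated purpose of expansion.

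**What to change.** In sections 11.3.2 and 11.4, for each opened histology:

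1. Tabulate primary-cohort patients (responders/m) and newly enrolled patients (responders/number enrolled) separately, with the response rate and Wilson 90% interval for the new patients. Their outcomes play no part in the opening rule, so this estimate is free of that bias.
2. Keep the pooled rate, but state that it includes the responders who triggered opening and that its Wilson interval is unadjusted for the opening rule. Put the same label on the section 11.3 table.
3. Describe N=10 as a sample size for estimation only, not as an A'Hern design.

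An interval conditional on opening may be added as an optional sensitivity analysis. If so, it should condition on the responder count actually used at the opening decision.

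The cost is a few lines of wording and one extra table per opened cohort, with no added patients and no changed decision rule. The downside is imprecision: new-patient intervals are wide when few are enrolled (1 of 2, as could arise with m=8, gives 12% to 88%), and there is no new-patient estimate when m is 10 or more.

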11.4 Methods of Analysis

Response criteria are described in Section 12. A responder is defined as a patient who achieves a best response of PR or CR on the study. Response rates will be calculated as the percent of evaluable patients who are responders, and confidence intervals will be constructed using the Wilson score interval method.³⁰ Decision making for A'Hern design cohorts will follow rules described above.

Any responses or lack thereof in patients enrolled during the determination of the Recommended Phase 2 Dose (dose finding phase) will count toward the objective response rate in their respective cohort.

Toxicity tables will be constructed to summarize the observed incidence by type of toxicity and grade. A patient will be counted only once for a given toxicity for the worst grade of that toxicity reported for that patient. Toxicity information recorded will include the type, severity, time of onset, time of resolution, and the probable association with the study regimen.

11.5 **Evaluability for Response**

Any eligible patient who is enrolled and receives at least one dose of protocol therapy will be considered evaluable for response. Any patient who receives non-protocol anti-cancer therapy during the response evaluation period will be considered a non-responder for the purposes of the statistical rule, unless they show an objective response prior to receiving the non-protocol anti-cancer therapy (in which case they will be considered a responder). Patients who demonstrate a complete or partial response confirmed by central review will be considered to have experienced a response. When opening expansion cohorts, the evaluation period for determination of best response will be 6 treatment cycles. All other patients will be considered non-responders. Patients who are not evaluable for response evaluation may be replaced for the purposes of the statistical rule. All patients considered to have a response (CR or PR) must have imaging studies reviewed centrally at the COG. Centers will be notified by the COG about requests for scans of patients with stable disease. Preliminary assessment of activity using institutionally provided tumor measurements will be entered into CDUS quarterly. The central review by COG will be provided as the final reviewed assessment of response when such becomes available.

11.6 **Evaluability for Toxicity**

All eligible patients who receive at least one dose of protocol therapy will be considered in the evaluation of toxicity. In addition, for the dose-escalation portion during Cycle 1, patients without DLT must receive at least 85% of the prescribed dose per protocol guidelines and must have the appropriate toxicity monitoring studies performed to be considered evaluable for toxicity for the purpose of determining dose escalation and defining the recommended phase 2 dose. Patients under [Section 4.1.7](#) are not evaluable for DLT if they do not experience a non-hematologic DLT.

11.7 **Progression free survival (PFS)**

Progression free survival will be defined as time from the initiation of protocol treatment to the occurrence of any of the following events: disease progression or disease recurrence or death from any cause. All patients surviving at the time of analyses without events will be censored at their last follow-up date.

PFS along with the confidence intervals will be estimated using the Kaplan-Meier method. Patients with local calls of disease progression (i.e. calls made by the treating institution), will be counted as having had an event, even if the central review does not declare progression. We will also report PFS based on central radiology review as a secondary analysis, if adequate number of disagreements in progressions exist between the treating institutions and the central radiology review to make such an analysis meaningful.

11.8 **Correlative Studies**

A descriptive analysis of pharmacokinetic (PK) parameters will be performed to define systemic exposure, drug clearance, and other pharmacokinetic parameters. The PK

parameters will be summarized with simple summary statistics, including means, medians, ranges, and standard deviations (if numbers and distribution permit).

A descriptive analysis of the exploratory aims described in [Section 1.3](#) will be performed and will be summarized with simple summary statistics. All of these analyses will be descriptive in nature.

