5.0 TREATMENT PROGRAM

5.1 Overview of Treatment Plan

Treatment Schedule Table	
Days 1-28	BVD-523FB (ulixertinib) orally twice daily
Day 28	Evaluation

Patients will receive BVD-523FB (ulixertinib) twice daily, continuously for 28-day cycles (please see dosing nomogram in [Appendix V](#)). Evaluations will occur at the end of every other cycle x 3, then every 3 cycles. A cycle may be repeated up to a total duration of therapy of 2 years (maximum 26 cycles).

Drug doses should be adjusted based on the BSA calculated from height and weight measured within 7 days prior to the beginning of each cycle. Take by mouth on an empty stomach either 1 hour before a meal or 2 hours after a meal. Capsules should not be opened, crushed or chewed. If a patient misses or vomits a dose of BVD-523FB (ulixertinib), an additional dose should not be taken. Patients should resume dosing at the next scheduled time.

Therapy will be discontinued if there is evidence of progressive disease or drug related dose-limiting toxicity that requires removal from therapy ([Section 6.0](#)). Therapy may otherwise continue for up to 2 years provided the patient meets the criteria for starting subsequent cycles ([Section 5.2](#)) and does not meet any of the criteria for removal from protocol therapy criteria ([Section 10.0](#)).

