7.5.3 BVD-523FB (ulixertinib) is a P-glycoprotein (P-gp) transporter substrate, and is highly protein bound (99-100% protein binding). Use caution in patients who are also receiving strong P-gp inhibitors (eg., amiodarone, carvedilol, clarithromycin, dronedarone, itraconazole, lapatinib, lopinavir and ritonavir, propafenone, quinidine, ranolazine, ritonavir, saquinavir and ritonavir, telaprevir, tipranavir and ritonavir, verapamil) or highly protein-bound drugs with narrow therapeutic ranges.

8.0 **EVALUATIONS/MATERIAL AND DATA TO BE ACCESSIONED**

8.1 **Required Clinical, Laboratory and Disease Evaluation**

All clinical and laboratory studies to determine eligibility must be performed within 7 days prior to enrollment unless otherwise indicated. Laboratory values used to assess eligibility (see [Section 4.0](#)) must be no older than seven (7) days at the start of therapy. Laboratory tests need **not** be repeated if therapy starts **within** seven (7) days of obtaining labs to assess eligibility. If a post-enrollment lab value is outside the limits of eligibility, or laboratory values are older than 7 days, then the following laboratory evaluations must be re-checked within 48 hours prior to initiating therapy: CBC with differential, bilirubin, ALT (SGPT) and serum creatinine. If the recheck is outside the limits of eligibility, the patient may not receive protocol therapy and will be considered off protocol therapy. Imaging studies, bone marrow aspirate and/or biopsy, must be obtained within 14 days prior to start of protocol therapy (repeat the tumor imaging if necessary).

STUDIES TO BE OBTAINED	Pre-Study	During Cycle 1	Prior to Subsequent Cycles [^]
History	X	Weekly	X
Physical Exam with vital signs	X	Weekly	X
Neurologic Exam	X		
Height, weight, BSA	X		X
Performance Status	X		
Pregnancy Test ¹	X		
CBC, differential, platelets	X	Twice Weekly (every 3 to 4 days) ^{2,3}	Weekly ^{2,3}
Urinalysis	X		
Electrolytes including Ca ⁺⁺ , PO ₄ , Mg ⁺⁺	X	Weekly	X
Creatinine, ALT, bilirubin	X	Weekly	X
Albumin	X		X
ECHO or gated radionuclide study	X		Every 3 cycles
EKG	X	End of Cycle 1	
Ophthalmologic Exam ¹⁰	X		
Tumor Disease Evaluation ^{4-A, 4-B, 4-C}	X		Every other Cycle x 3 then q 3 Cycles ⁴
Plain radiograph tibial growth plate (bone x-ray tests) ¹¹	X		Prior to Cycles 2 and 5, then every 6 months
Bone Marrow Aspirate and/or biopsy ^{5,6}	X ⁶		
Medication Diary ⁷		Weekly	X
Pharmacokinetics (optional) ⁸		X	

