10.0 CRITERIA FOR REMOVAL FROM PROTOCOL THERAPY AND OFF STUDY CRITERIA

10.1 Criteria for Removal from Protocol Therapy

- a) Clinical (including physical examination or serum tumor markers) or radiographic evidence of progressive disease (See [Section 12](#)).
- b) Adverse Events requiring removal from protocol therapy (See [Section 6](#)).
- c) Refusal of protocol therapy by patient/parent/guardian
- d) Non-compliance that in the opinion of the investigator does not allow for ongoing participation.
- e) Completion of 26 cycles of therapy.
- f) Physician determines it is not in the patient's best interest.
- g) Repeated eligibility laboratory studies (CBC with differential, bilirubin, ALT (SGPT) or serum creatinine) are outside the parameters required for eligibility prior to the start of protocol therapy (See [Section 8.1](#)).
- h) Study is terminated by Sponsor.
- i) Pregnancy
- j) Patient did not receive protocol treatment after study enrollment

Patients who are removed from protocol therapy during cycle 1 should continue to have the required observations in [Section 8.1](#) until the originally planned end of the cycle or until all adverse events have resolved per [Section 13.4.4](#), whichever happens LATER. The only exception is with documentation of the patient's withdrawal of consent from the APEC1621SC screening protocol. Patients who are removed from protocol therapy in subsequent cycles should have the necessary observations to ensure adequate clinical care.

10.2

Follow-Up Data Submission and APEC1621SC Off Study Criteria

Patients who are off subprotocol therapy will continue to be followed on the APEC1621SC screening protocol. Follow-up data submission will occur until one of the APEC1621SC Off Study Criteria is met (See Section 10 of APEC1621SC for details). Ongoing adverse events, or adverse events that emerge after the patient is removed from protocol therapy, but within 30 days of the last dose of investigational agent, must be followed and reported via RAVE and CTEP-AERS (if applicable). Follow-up data will be required until off study criteria are met unless consent is withdrawn or the patient dies or is lost to follow-up.

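### PFS is censored at last follow-up rather than at the last disease evaluation, and no tumor evaluations are scheduled here after therapy stops, so PFS may be overestimated unless APEC1621SC records dated progression

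*Combined protocol and SAP*

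**What the plan says.** Section 11.7 sets the time origin and the events: "Progression free survival will be defined as time from the initiation of protocol treatment to the occurrence of any of the following events", namely progression, recurrence or death from any cause. The estimator is descriptive: "PFS along with the confidence intervals will be estimated using the Kaplan-Meier method". For patients without an event, "All patients surviving at the time of analyses without events will be censored at their last follow-up date". On who calls progression, "Patients with local calls of disease progression (i.e. calls made by the treating institution), will be counted as having had an event", even if central review disagrees.

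The evaluation schedule runs on treatment cycles. Section 5.1 states: "Evaluations will occur at the end of every other cycle x 3, then every 3 cycles". The table in Section 8.1 repeats this as "Every other Cycle x 3 then q 3 Cycles".

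Section 10.1 lists several ways to leave therapy without progression: toxicity, refusal, non-compliance, physician decision, and completion of 26 cycles. It asks patients removed during cycle 1 to keep the required observations at least to the planned end of that cycle. For later removals it says only: "Patients who are removed from protocol therapy in subsequent cycles should have the necessary observations to ensure adequate clinical care". Section 10.2 then adds: "Patients who are off subprotocol therapy will continue to be followed on the APEC1621SC screening protocol". It refers to Section 10 of APEC1621SC for when that follow-up ends. APEC1621SC is not among the documents reviewed.

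**The concern.** The censoring date and the assessment schedule follow different clocks. The censoring clock runs to last contact, wherever that contact is recorded. The assessment clock in this document stops with therapy.

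Take a patient who stops for toxicity at month 3 with stable disease and was last known alive at month 14. If progression at month 5 is never recorded, the rule in Section 11.7 counts 14 progression-free months. The last evaluation supports only about 3.

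An error of this kind can only lengthen PFS. The trial has a single arm and a primary cohort of 20, so there is no control group to share the distortion, and PFS would naturally be read against outside experience.

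**Working it through.** **No stated figure to reproduce.** The plan gives no assumed median, event count, precision target or test for PFS. The steps below are an illustration, and every input in step 1 is an assumption.

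**1. Inputs (assumed)**
- Time to progression is exponential with median 4 months: λ = ln2/4 = 0.1733 per month.
- Progression to death is exponential with median 12 months: δ = ln2/12 = 0.0578 per month.
- Leaving therapy without progression is exponential and independent of prognosis: μ = 0.044 or 0.10 per month. The share leaving before progression is μ/(μ+λ): 0.044/0.2173 = 20% and 0.10/0.2733 = 37%.
- All patients are followed for 18 months, so nobody is censored before month 6 under the rule as written.
- Progression after leaving therapy is captured with probability c. If it is missed, the next event is death.

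**2. True 6-month PFS**

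exp(−6λ) = 2^(−1.5) = 35.4%.

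**3. Rule as written, c = 0**

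The excess is the probability that a patient left therapy, then progressed unseen before month 6, and is still alive at month 6:

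λ·exp(−6δ)·{[1−exp(−6(λ−δ))]/(λ−δ) − [1−exp(−6(λ+μ−δ))]/(λ+μ−δ)}

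Here λ·exp(−6δ) = 0.1733 × 0.7071 = 0.1225, and the first bracket is 0.5/0.1155 = 4.328.

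- μ = 0.044: the second bracket is 3.862. Excess = 0.1225 × 0.466 = 5.7 points, so 6-month PFS is 41%.
- μ = 0.10: the second bracket is 3.367. Excess = 0.1225 × 0.961 = 11.8 points, so 6-month PFS is 47%.

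**4. Partial and full capture**

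The excess scales with (1−c).

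| Off-therapy progression captured | 20% leave | 37% leave |
|---|---|---|
| None | 41% | 47% |
| Half | 38% | 41% |
| All | 35% | 35% |

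**5. The amended rule, c = 0**

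Patients who leave and have no recorded event are censored at their last scan (simulated with scans every 1.84 months, which is two 28-day cycles). Later deaths stay as events. Simulation gives 36.8% (20% leaving) and 39.0% (37% leaving). The upward error falls from about 6 and 12 points to about 1.5 and 3.5 points. With full capture, both rules give the true value.

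**6. Sensitivity to the assumptions**

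A second simulation used the protocol's own scan times (after cycles 2, 4 and 6, then every 3 cycles). It assumed median time to progression of 3 or 6 months, 10% to 30% leaving without progression, and a 6-month median from progression to death. The reference was continued scanning for everyone.
- No capture: the plan's rule adds about 1.5 to 13 points at 6 months and 3 to 14 points at 12 months.
- Half captured: it adds about 1 to 7 points at both times.
- Full capture: it adds nothing.
- The median moved in only one of the no-capture scenarios (3-month median, 30% leaving: 3.7 to 5.3 months). The effect on PFS at fixed times is the firmer result.

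**The case against.** The strongest reply is that APEC1621SC may already supply what is missing. Section 10.2 keeps patients under follow-up there, and if that protocol records dated progression the present rule is unbiased. A reader might infer from Section 11.7 alone that PFS is certainly biased upward, or that the rule is inferior whatever APEC1621SC collects. The documents support neither inference: the follow-up content is unseen, and with full capture the two rules agree.

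Zero capture is also an extreme case. Local progression calls count with no restriction to time on therapy. A note to the table in Section 8.1 lets the investigator rely on clinical or laboratory evidence without a confirming scan. Deaths count. The note in Section 12.4.3 asks for objective progression to be documented after treatment stops, though only for symptomatic deterioration. These points stand, and they make the upper figures a ceiling.

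A reader might also take the 65% in Section 2.3.1 as evidence that many patients will leave early. That figure counts dose interruptions in adults regardless of attribution, alongside a median dose intensity of 89%. It is not a discontinuation rate, and the documents give none.

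Finally, precision is low. With 20 patients a 35% estimate has an approximate 95% half-width of 1.96 × √(0.35 × 0.65/20) = 21 points. With 49 it is 13 points. The possible bias therefore lies within sampling error. That limits the consequence, but it does not justify leaving an avoidable one-directional error in place.

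**Conclusion.** The concern holds in conditional form. Section 11.7 does not tie the censoring date to a disease evaluation, and this document sets no tumor-evaluation schedule after therapy stops. Unless APEC1621SC records dated progression status, PFS may be overestimated.

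Under the stated assumptions the error in 6-month PFS runs from zero (full capture) through about 3 to 6 points (half captured) to about 6 to 12 points (none captured). Its direction is upward or nil. The exit rates, the progression and survival times, and the capture rate are all assumed.

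PFS is a secondary, descriptive endpoint. The response-rate rule in Section 11.3 does not use it and is unaffected.

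**What to change.** Replace the censoring sentence in Section 11.7 with: *Patients without progression, recurrence or death are censored at the date of their last disease evaluation showing no progression (including evaluations recorded on APEC1621SC).* Keep censoring at last follow-up as a sensitivity analysis. A wide gap between the two estimates would show that off-therapy ascertainment is incomplete.

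The cost is one sentence of analysis text, since this protocol already collects its own evaluation dates. There are two downsides: follow-up becomes slightly shorter, and some informative censoring enters if patients who stop early differ in prognosis. The change does not remove the bias entirely. Deaths after an unrecorded progression remain events at the date of death, which is why about 37% to 39% against 35% is left when nothing is captured.
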